12.2 Data analysis

Data collection and analyses will include maternal and infant demographics; breastfeeding outcomes (at discharge, 6-8 weeks and 4 months); length of stay; maternal-infant attachment; maternal satisfaction and perceptions relating to enabler use; staff time to recruit and educate families, perceptions relating to intervention impact and adverse events; and maternal and

staff awareness of safe sleep recommendations (self reported and observed). Data from this pilot, the first Australian trial of a hospital postnatal safe sleep enabler, will be used to inform a randomised controlled trial of safe sleep enablers in postnatal environments.

Maternal Data: Analysis of maternal data will be conducted using the principles of intention to treat. All participants who were enrolled and randomly allocated to treatment are included in the analysis and will be analysed in the groups to which they were randomised. A further analysis will be based on actual use, consistent with a recent published study on Wahakura use, a Maori safe sleep enabler, intended for domestic use after discharge home to the community (Baddock et al., 2017) which performed analyses based on intention to treat and actual use.

Statistical analyses will be performed to report the prevalence and proportions of variables surveyed. Questionnaire results will be entered into a purpose-built Microsoft Excel database for data cleaning and preparation for statistical analysis. A 10% random selection (approximately 9-10 questionnaires from each of the maternal records, staff survey and audits) will be double entered to assess data-entry accuracy and intra-rater reliability. Consistency checks will be performed on all variables to ensure that only valid responses will form the basis of the ensuing analysis.

Quantitative data will be analysed using descriptive techniques such as frequency and percentage and measures of central tendency and distribution (for example, mean and standard deviation or median and IQR). Normality of data will be assessed. Group comparisons to comparing equivalency of control and interventions will be conducted with Chi-squared test for categorical measures and analysis of variance or Kruskal-Wallis test for continuous measures as appropriate assessing for normality and equality of variances.

Staff Survey Data: Should continuous data be distributed symmetrically, then means and standard deviation (SD) will be reported. Medians, inter-quartile ranges (IQR), frequencies and percentages will be used to report the central tendency, spread and empirical distributions of categorical and non-symmetric continuous variables elicited at each survey. All bivariate comparisons of categorical frequencies will be undertaken using Fisher's exact test, log-linear and logistic models, while McNemar's test and Agresti's test of symmetry will be used to detect differences between participants' responses at any two survey points (pretest vs post-test). Continuous data will be analysed using Student's t-test, Student's paired t-test, ANOVA or using their nonparametric equivalents (should the data exhibit non-normality).

Audit data: All qualitative data will be coded prior to data entry. Frequency data will be reported and analysed using standard categorical techniques (accounting for the matched nature of the data between mother and baby). Univariate linear modelling will be conducted for dependent variables that will include infant sleep position, infant placement in the cot, placement and securement of bedding; and presence of particular objects in the cot, e.g. Infant quilts, toys, cot bumpers.

All statistical comparisons will be analysed using the SAS or SPSS statistical software package (IBM Corp 2013). A value of $p=0.05$ will be used to define statistical significance for primary outcomes as they are independent of each other. We recognize that there are a large number of secondary outcomes and will report uncorrected p values with a nominal level of significance of 0.05.

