5. HYPOTHESES

5.1 Primary Hypotheses

The priority of the pilot is to test the novel concept of safe sleep enablers for the first time in an Australian setting. Two primary hypotheses will focus on maternal acceptability of the safe sleep enablers as alternative infant sleep spaces and the feasibility of the proposed protocol in a busy maternity setting.

The primary hypotheses are:

1. Acceptability with infant safe sleep enablers will be demonstrated by mothers in the maternity unit setting.
2. Feasibility of a pilot protocol to evaluate safe sleep enablers in the maternity unit setting will be demonstrated (as measured by staff support, appropriate application of the protocol: consent, randomisation, documentation processes).

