If the allocated cot is not available (i.e. the First Days Pepi-Pod® or MaBim are already in use) the participant will be allocated to a standard cot. These allocations will be managed as a fourth group in the analysis in which demographic information should theoretically be similar to the standard cot allocated group. This method also serves as an internal checking procedure for the randomisation process used in the clinical environment. In this instance, the midwife in charge will make an entry in the Project Register for participant name, envelope number, first cot allocation, non-availability and reallocation to standard cot and will place the envelope into the discard box (to allow checking of integrity of the randomisation process).

A total of 300 envelopes will be prepared representing each of the three options equally (100/100/100) and which will also allow for the envelope discard process. A mock run of the randomisation process indicated that based on an estimated 7 deliveries per day and an average stay of 3 days, the four MaBim cots would be in almost constant use and approximately half of those mother-baby pairs randomised to the MaBim would be allocated

to use them. This process will allow integrity of the randomisation of process while still maintaining recruitment for each target sample within a feasible timeframe.

An allocation to a cot is intended for the duration of hospitalisation. The usual length of hospital stay for a woman having a vaginal delivery is 1-3 days; for a woman delivering by caesarean section 3-5 days. Analyses will be by Intention to Treat according to actual allocation and Actual Use, consistent with a recent randomised controlled study of safe sleep enabler use (Baddock et al., 2017).

The study will continue until there is a minimum of 60 participants in each group (total n=180) and will allow an attrition rate of up to 50% during the 4 month follow-up period following discharge from the post-natal unit. The final target sample for this pilot is 30 participants in each group with a complete data set.

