11.4 Measurement tools used

Data collection tools developed for this study have been based on previously used tools, including those recommended in the literature, including:

- ICHOM Pregnancy and Childbirth standard set (ICHOM, 2016) which includes questions relating to breastfeeding outcomes, maternal-infant attachment and maternal satisfaction (Dennis, 2003, Taylor et al., 2005);
- New Zealand First Days Pod evaluation tool (Cowan, 2016);
- Queensland Indigenous Pēpi-Pod® Program evaluations (Young, 2016; Young et al., 2016);
- Published breastfeeding evaluation tools, Breastfeeding Self-Efficacy Scale-Short Form (BSES-SF) (Dennis, 2003) and the Breastfeeding success variable (ICHOM, 2016);
- Queensland Nursing and Midwifery Knowledge, Attitudes and Practices relating to risk for SUDI (Young and Schluter, 2002; Young and O'Rourke, 2003; Young et al., 2008);
- Safe Sleep Education Project Survey and Practice Audit Tools (Young et al., 2010);
- Queensland Infant Care Practice Study (Schluter and Young, 2002; Young et al 2008).

Additional questions have been developed to address specific outcomes of this pilot where no pre-existing tool was available. Please see Table 1 for the outcomes that will be measured.

Table 1: Proposed outcome, measurement tool and time point of data collection

Outcome	Measurement tool	Time point	Person responsible
Maternal and neonatal demographic data	Client Health Record	≥ 36 weeks of gestation AND after birth	Research Assistant, Registered Midwife
Breastfeeding Method	Breastfeeding success variable (ICHOM, 2016)	≤ 3 days / prior to discharge (immediate rate) AND 6-8 weeks (medium rate) AND	Research Assistant, Registered Midwife

		4 months (long term rate)	
Breastfeeding self-efficacy	Breastfeeding Self-Efficacy Scale-Short Form (BSES-SF) (Dennis, 2003)	≤ 3 days / prior to discharge (immediate rate) AND 6-8 weeks (medium rate) AND 4 months (long term rate)	Research Assistant, Registered Midwife
Maternal acceptability of the SSD or control	Questionnaire (author developed)	≤ 3 days / prior to discharge	Research Assistant, Registered Midwife
Staff acceptability of the SSD or control	Questionnaire (author developed)	Approx. 16-20 weeks after study commencement	Research Assistant, Registered Midwife
Maternal-infant attachment	Mother-to-Infant Bonding Scale (MIBS) (Taylor et al., 2005, ICHOM, 2016)	≤ 3 days / prior to discharge AND 6-8 weeks AND 4 months	Research Assistant, Registered Midwife

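### Sections 11.3 and 12.2 disagree on where mothers who drew a MaBim but were given a standard cot are analysed, and neither names the analysis that decides the primary acceptability outcome

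*Protocol*

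**What the plan says.** **The outcome.** The first primary hypothesis (Protocol section 5.1) reads "Acceptability with infant safe sleep enablers will be demonstrated by mothers in the maternity unit setting". Section 10.1 lists mothers' acceptability of the enabler as a primary outcome. Table 1 in section 11.4 measures "Maternal acceptability of the SSD or control" with an author-developed questionnaire at or before discharge.

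**Supply.** Section 11.3 provides four MaBim cots and 15 Pēpi-Pods, and every bed has a standard cot. Envelopes are split equally between three options. If the drawn device is in use, "the participant will be allocated to a standard cot". A mock run with 7 deliveries a day and a 3-day stay led the authors to expect that "approximately half of those mother-baby pairs randomised to the MaBim would be allocated" one.

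**Analysis, section 11.3.** On the reallocated mothers: "These allocations will be managed as a fourth group in the analysis". On the analysis as a whole: "Analyses will be by Intention to Treat according to actual allocation and Actual Use".

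**Analysis, section 12.2.** Maternal data follow intention to treat, and all randomised mothers "will be analysed in the groups to which they were randomised". No outcome is exempted. The section then adds: "A further analysis will be based on actual use".

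**The concern.** Acceptability is a rating of an object. A mother who drew a MaBim and was given a standard cot has only the standard cot to rate. Section 12.2 counts her rating in the MaBim group, whereas section 11.3 keeps it out. The MaBim figure for a primary outcome therefore depends on which section the analyst follows.

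A single rule for all outcomes does not solve this. Analysis by randomised group suits breastfeeding, attachment, length of stay and safety, but it mixes two objects in a device rating. A fourth group gives a clean device rating, but it takes randomised mothers out of the MaBim arm for every other outcome. The mixing also falls almost wholly on one device, because Pēpi-Pods are seldom out of stock. Under section 12.2 the two devices would not be scored on the same footing.

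**Working it through.** **1. Reproduce the mock run.** Inputs from section 11.3: 7 arrivals a day, one third drawing MaBim, a 3-day stay and 4 cots. The offered load is a = 7 × 1/3 × 3 = 7 cots. The chance that all c cots are in use (Erlang loss formula) is B = (a^c/c!) / Σ(a^k/k!), k = 0 to c.

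- Numerator: 7⁴/24 = 100.04
- Denominator: 1 + 7 + 24.5 + 57.17 + 100.04 = 189.71
- B = 0.527

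So 52.7% are not supplied and 47.3% are, which agrees with the protocol's statement of about half. A simulation with a fixed 3-day stay also gave 52.7% not supplied.

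**2. Pēpi-Pod on the same inputs.** With a = 7 and c = 15, B = 0.3%.

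**3. Enrolment from section 12.1.** The mock run treats every delivery as a participant. Section 12.1 expects 30-40 eligible births a week and 40% participation, so 12-16 mothers a week. The stay is assumed to be 3 days.

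| Mothers per week | Load a = (n/7) × 1/3 × 3 | MaBim not supplied |
|---|---|---|
| 12 | 1.71 | 6.7% |
| 16 | 2.29 | 12.6% |

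With mean stays of 2 to 4 days the range widens to 2-21%.

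**4. Effect on the acceptability figure.** Let q be the share not supplied, d the acceptability of the MaBim and s that of the standard cot. Assume that reallocated mothers rate the standard cot as control mothers do. Under section 12.2 read literally:

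- MaBim-arm figure = (1 − q)d + qs
- MaBim-versus-standard contrast = (1 − q)(d − s)

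The contrast keeps 47% of its size at q = 0.527 and 87-93% at q = 0.13 to 0.07. This proportion does not depend on d or s.

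**5. Percentage points, for illustration only.** The documents give neither d nor s. Take d = 86%, borrowed from the would-recommend figure for the First Days Pēpi-Pod in section 9.7, and vary s.

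| s (assumed) | Figure at q = 0.5 | Figure at q = 0.07 | Figure at q = 0.13 |
|---|---|---|---|
| 50% | 68% | 83.5% | 81.3% |
| 70% | 78% | 84.9% | 83.9% |
| 86% | 86% | 86% | 86% |
| 90% | 88% | 86.3% | 86.5% |

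If instead d = 60% and s = 86%, the figure at q = 0.5 is 73%, which flatters the MaBim.

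**6. The alternative rule.** With the reallocated mothers kept as a fourth group, q = 0 and no mixing occurs.

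**The case against.** Four points can be made against the concern.

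- **Other analyses are planned.** A reader might infer that the trial would report no true MaBim acceptability at all. The documents do not support that. Section 11.3 sets the reallocated mothers apart, and section 12.2 follows its intention-to-treat rule with an actual-use analysis. This objection stands against the stronger reading, but it does not settle which result decides the outcome. Actual use is also undefined. Since every bed has a standard cot, a mother who was supplied a MaBim and gave it up could be classed as a non-user, which would remove the very mothers who found it unacceptable.
- **Nothing is selected on this result.** A reader might infer that acceptability chooses the device for the larger trial. No section says so. Section 12.1 plans 454 per group and 1,362 in total, and 3 × 454 = 1,362, so three groups. The primary hypothesis also speaks of enablers collectively, with no threshold per device. This stands in full.
- **The practical size may be small.** If 180 mothers are randomised over 4-6 months (about 7-10 a week, 3-day stay assumed), non-availability is only about 1.5-4.7%. At an assumed 86%, the 95% half-width is about 12 points with 30 mothers and 9 points with 60, so dilution at these rates lies well inside sampling error. This stands, although the figure of about half is the protocol's own.
- **Populations can be left to the analysis plan.** That would answer an omission. Here two sections of the protocol give different rules for the same mothers.

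**Conclusion.** The point holds as an inconsistency that affects a primary outcome. Sections 11.3 and 12.2 assign the reallocated mothers differently, and neither names the deciding analysis for acceptability. Under section 12.2 read literally, about half of the MaBim arm (mock-run inputs) or about 7-13% of it (section 12.1 enrolment, 3-day stay assumed) would be rating a standard cot, against under 0.5% for the Pēpi-Pod. The contrast with the standard cot shrinks by the same share, provided reallocated mothers rate that cot as controls do. It would be wrong to infer that MaBim acceptability will be understated: the direction and size in percentage points depend on standard-cot acceptability, which the documents do not give.

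**What to change.** Reconcile sections 11.3 and 12.2 by outcome.

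- **Device ratings** (maternal acceptability, satisfaction with the enabler): name as primary the analysis of all mothers randomised to the device and supplied with it, including those who later stopped using it. Report a proportion with a 95% CI for each device.
- **Non-availability**: report the share who drew a device that could not be supplied as a feasibility proportion, from the Project Register.
- **Breastfeeding, attachment, length of stay and safety**: keep analysis by randomised group, with reallocated mothers in the arm they drew.
- **Actual use**: define it, and label that analysis as supportive.

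The change is wording only, since section 11.3 already has non-availability and reallocation entered in the Project Register. The cost is a smaller MaBim denominator. If 60 mothers were randomised to the MaBim and half were supplied, the 95% half-width at an assumed 86% would go from about 9 points (n = 60) to about 12 (n = 30). At 7-13% not supplied it would barely change.

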13. ETHICAL CONSIDERATIONS

The ESCCaPE trial is a collaboration between the Sunshine Coast Hospital and Health Service, the University of the Sunshine Coast and Change for Our Children Ltd.

Ethical approval has been acquired from the Royal Brisbane and Women's Hospital Human Research Ethics Committee. For ethical concerns regarding the conduct of this study please contact: Human Research Ethics Office, Royal Brisbane and Women's Hospital, [name]. [contact]. Email: [contact] .

This trial requires voluntary participation. Informed consent will be gained from all participants. Participants are free to withdraw at any time.

In the case of injury to participants during the course of the study, participants will be insured as patients of the Sunshine Coast Hospital and Health Service. Liability of participants is stipulated in the collaborative research agreement, signed by all parties prior to gaining governance approval.

The researchers are guided by The National Statement on Ethical Conduct in Human Research (NHMRC 2007 updated 2015). Ethical principles of research merit and integrity, justice, beneficence and respect will be upheld at all times by the researchers (NHMRC 2007 updated 2015).

14. DISSEMINATION OF RESULTS AND PUBLICATIONS

Members of this research team have led the first trial of the Queensland Pēpi-Pod® Program in collaboration with NZ Change for our Children so are ideally positioned to build on this work in an Australian context and to disseminate findings to key stakeholders through existing networks.

Relevant findings will be shared with key stakeholders and collaborators, including:

- SCUH Hospitals and Health Services
- Queensland Paediatric Quality Council and the QPQC Infant Mortality Subcommittee
- QH Statewide Maternal and Neonatal Network
- State Coroner, [name] and Brisbane Coroner, [name]
- Commissioner Queensland Family and Children's Commission
- Department of Product Safety, Office of Fair Trading
- Patient Safety and Quality Improvement Service, Queensland Health
- Red Nose Foundation
- Change for our Children Ltd, New Zealand
- And, all who have been briefed and indicated support for the Pēpi-Pod Program concept.

15. OUTCOMES AND SIGNIFICANCE

The significance of this study is that it addresses two internationally identified health priorities of relevance to Queenslanders, is timely, is innovative in this practice context, and addresses current clinical practice and safety issues experienced by the local SCHHS. It will also provide new knowledge that has the real potential to influence practice and care delivery to families with newborns at a state and national level.

The aims of this study address two public health priorities, recognised nationally and internationally (WHO, 2016): 1) the support of breastfeeding which is vital to reducing the burden of disease and mortality experienced by Australians; and 2) reducing infant mortality and morbidity.

This study will constitute the first trial of a safe sleep enabler in an Australian postnatal setting. Evaluations of innovative interventions which are designed to support breastfeeding and enhance safety of sleeping environments is an area which has been identified as a priority for investigation by organisations, clinicians and parent groups. These groups are committed to supporting safe, practical, and culturally appropriate safe infant care practices and role modelling safe sleep behaviours for parents in an effort to reduce infant mortality and morbidity (Dodd 2012; SIDS and Kids, 2015; Young et., 2012).

Health services have a responsibility to follow through from simply informing about safe infant sleep practice to enabling safe infant sleep action (Cowan et al., 2012). Safe sleep enablers such as the NZ Pēpi-Pod® First Days Pod and the MaBim Side-car Crib (Italy, Directive 93/42/CEE) draw attention away from problems for vulnerable babies in unsafe sleeping situations and instead focuses on a solution; support for parents and protection for the baby. Local SCHHS data also support the need to address safety issues relating to infant falls from adult postnatal beds in ways that support breastfeeding and safe infant sleeping.

The Australian Department of Product Safety, Office of Fair Trading have offered in principle support and collaboration to this investigation. The Department are currently reviewing and developing safety guidelines for side-car co-sleepers for domestic use, and have offered their support in reviewing the proposed sleep spaces for this study, given both devices meet safety standards in other countries (Change for our Children NZ Pēpi-Pod First Days Pod, New Zealand; MaBim neonatal cot for co-sleeping, Italy) as there are currently no Australian-based commercial co-sleeping cots for post-natal hospital environments. This study therefore offers a timely opportunity for clinicians and researchers to contribute directly to guidelines for product safety development. This study provides an opportunity for SCHHS to lead the way in Australian maternity services in the introduction of innovative practices in health service delivery to mothers and their newborns; which is timely given the opening of the new maternity facility at the Sunshine Coast University Hospital in 2017.

It is anticipated that the findings of this pilot will provide the platform for a randomised controlled trial. The RCT would aim to provide high quality evidence for the effectiveness of postnatal safe sleep enablers in improving optimal breastfeeding outcomes and parental uptake of safe sleep behaviours to reduce the risk of SIDS.

This pilot study will have a local and national impact. Health professionals play an integral role in promoting public health messages through role modelling, parent education and

supporting evidence-based guidelines, hospital policies and procedures. Local impact for SCHHS clients includes improving breastfeeding outcomes and maternal satisfaction with care received; increasing culturally appropriate and personal options and choice in care accessed; reduced adverse events associated with baby falls from maternal beds, or in chairs; improved uptake of safe sleeping recommendations as parents' transition to home environments; and development of evidence-based policies, procedures and associated parent education that support breastfeeding and safe infant sleeping. Key impact also, is the support of SCCHS staff to address current clinical safety issues in providing safe infant sleep environments that promote breastfeeding in the immediate postnatal environment and developing research capacity through participation in clinical research.

Feasibility of increasing reach of these study findings at state and national levels is optimised through the existing collaborations between the research team and organisations and government departments with an interest in reducing infant deaths and promoting optimal infant care. These include the current Queensland Pēpi-Pod Program®, Red Nose; Australian College of Midwives; the State Coroner; Office of Fair Trading, Department of Product Safety; Queensland Family and Child Commission; Queensland Maternity and Neonatal Network; Qld Paediatric Quality Council, and the Qld Child Death Review Panel.

Originality: There is a paucity of evidence on the use of postnatal safe sleep enablers and no published literature on use in an Australian setting; this will be the first study evaluating a safe sleep enabler in an Australian postnatal setting.

Feasibility: Members of this research team have led the first trial of the Queensland Pēpi-Pod® Program in collaboration with NZ Change for our Children so are ideally positioned to build on this work in an Australian context and to disseminate findings to key stakeholders through existing networks.

